6.2.2. Secondary Endpoints

The key secondary endpoints are:

- CR rate (CR defined as bone marrow blasts <5% and no Auer rods, absence of extramedullary disease, ANC $\geq 1.0 \times 10^9/L$ [1000/ μL], platelet count $\geq 100 \times 10^9/L$ [100,000/ μL], and independence of RBC transfusions).
- OS, defined as the time from date of randomization to the date of death due to any cause.
- CR + CRh rate (CRh is defined as a CR with partial recovery of peripheral blood counts where ANC is $>0.5 \times 10^9/L$ [500/ μL], and platelet count is $>50 \times 10^9/L$ [50,000/ μL]; CRh will be derived by the Sponsor).
- ORR, defined as the rate of CR, CRi (including CRp), PR, and MLFS.

Additional secondary endpoints are:

- CR + CRi (including CRp) rate (CRi [including CRp] is defined as all CR criteria except for residual neutropenia where ANC is $<1.0 \times 10^9/L$ [1000/ μL] or thrombocytopenia where platelet count is $<100 \times 10^9/L$ [100,000/ μL]; without platelet transfusion for at least 1 week prior to disease assessment).
- DOCR, among subjects who achieved CR; DOCRh, among subjects who achieved CR or CRh; DOR, among subjects who achieved CR, CRi (including CRp), PR, and/or MLFS; and DOCRi, among subjects who achieved CR or CRi (including CRp).

- TTCR, among subjects who achieved CR; TTCRh, among subjects who achieved CR or CRh; TTR, among subjects who achieved CR, CRi (including CRp), PR, and/or MLFS; and TTCRi, among subjects who achieved CR or CRi (including CRp).
- Vital signs, and results of ECOG PS, ECG, and echocardiogram (ECHO) or multi-gated acquisition (MUGA) for left ventricular ejection fraction (LVEF) as clinically indicated (method per institutional standard of care, with the same method used for an individual throughout the study; sites in Germany may only use ECHO).
- Clinical laboratory assessments (hematology, chemistry, and coagulation).
- AEs, AEs of special interest (AESIs), SAEs, and AEs leading to discontinuation or death.
- Concomitant medication use.
- Transfusion requirements (platelet and RBC; number of units transfused), rates of infection, days spent hospitalized, and other efficacy and safety measures that are potentially indicative of clinical benefit.
- Changes from baseline in QoL assessments (EORTC QLC-C30 and EQ-5D-5L).
- Rates of CR with IDH1 MC.
- AG-120/placebo and azacitidine drug exposure, including dose modifications and dose intensities.
- AG-120 and 2-HG concentrations in circulating plasma.

[REDACTED]

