Abbreviations: CR = complete remission; CRh = CR with partial hematologic recovery; EFS = event-free survival; IV = intravenous; ORR = objective response rate; OS = overall survival; PO = oral; Q = every; QD = once daily; ROW = Rest of World; SC = subcutaneous.

Subjects should be treated for a minimum of 6 cycles of combination therapy unless they experience relapse after achieving a CR, CRi (including CRp), or MLFS; disease progression prior to achieving CR, CRi (including CRp), or MLFS; unacceptable toxicity (AE); confirmed pregnancy; withdrawal by subject; protocol violation; death; or End of Study.

Treatment will be administered as follows:

- All subjects will receive azacitidine 75 mg/m²/day SC or IV for the first week (7 days) (or on a 5-2-2 schedule) of each 4-week (28-day) cycle in combination with AG-120 or placebo QD on each day of the 4-week cycle. The same schedule should be used for each subject throughout the duration of treatment, when possible.
- Subjects should continue to receive therapy with AG-120 or placebo + azacitidine until death, disease relapse, disease progression, development of unacceptable toxicity (adverse event), confirmed pregnancy, withdrawal by subject, protocol violation, or End of Study (defined in Section 9.11.1).
 - Disease progression (defined only for subjects who have not previously attained CR, CRi, CRp, or MLFS) is defined as evidence for an increase in bone marrow blast percentage and/or increase of absolute blast counts in the blood: 1) >50% increase in bone marrow blast count over baseline (a minimum 15% point increase is required in cases with <30% blasts at baseline); or persistent marrow blast percentage of >70% over at least 3 months; without at least a 100% improvement in ANC to an absolute level (> 500/μL, and/or platelet count to >50,000/μL non-transfused); 2) >50% increase in peripheral blasts (white blood cells [WBCs] × % blasts) to >25,000/μL in the absence of treatment-related differentiation syndrome; or 3) new extramedullary disease.

- Subjects with a response less than CR at 24 weeks or beyond can continue on treatment if demonstrating treatment benefit, defined as any of the following: 1) Transfusion-independence while on study treatment; 2) ANC >500/ μ L; or 3) platelets >50,000/ μ L.

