Table 10: Modified International Working Group Response Criteria for Acute Myeloid Leukemia

Category	Definition
Complete remission (CR) ^a	Bone marrow blasts <5% and no Auer rods; absence of extramedullary disease; ANC $\geq 1.0 \times 10^9/L$ (1000/ μ L); platelet count $\geq 100 \times 10^9/L$ (100,000/ μ L); independence of red blood cell transfusions
CR with incomplete recovery (CRi), including CR with incomplete platelet recovery (CRp) ^b	All CR criteria except for residual neutropenia (ANC < $1.0 \times 10^9/L$ [1000/ μ L]) or thrombocytopenia (platelet counts < $100 \times 10^9/L$ [100,000/ μ L]; without platelet transfusion for at least 1 week prior to disease assessment)
Morphologic leukemia-free state (MLFS)	Bone marrow blasts <5% and no Auer rods; absence of extramedullary disease; no hematologic recovery required
Partial remission (PR)	All hematologic criteria of CR; decrease of bone marrow blast percentage to 5%-25%; and decrease of pretreatment bone marrow blast percentage by at least 50%
Relapse (defined only for subjects who have previously attained CR, CRi, CRp, or MLFS) ^c	Bone marrow blasts $\geq 5\%$; or reappearance of blasts in the blood; or development of extramedullary disease

Source: (Cheson et al. 2003; Döhner et al. 2017; Sievers et al. 2001).

Abbreviations: AML = acute myeloid leukemia; ANC = absolute neutrophil count; IWG = International Working Group; MDS = myelodysplastic syndrome.

Note: Modified to remove molecular complete remission (CRm) and cytogenetic complete remission (CRc).

^a All criteria need to be fulfilled; marrow evaluation should be based on a count of 200 nucleated cells in an aspirate with spicules; if ambiguous, consider repeat exam after 5 to 7 days; flow cytometric evaluation may help to distinguish between persistent leukemia and regenerating normal marrow; a marrow biopsy should be performed in cases of dry tap, or if no

spicules are obtained; no minimum duration of response required. ANC $\geq 1.0 \times 10^9/L$ (1000/ μL) per the European LeukemiaNet guidelines.

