^b The criterion of CRi is of value in protocols using intensified induction or double induction strategies, in which hematologic recovery is not awaited, but intensive therapy will be continued. In such protocols, CR may even not be achieved in the course of the entire treatment plan. In these instances, the overall remission rate should include CR and CRi subjects. Some subjects may not achieve complete hematologic recovery upon longer observation times. CRi includes subjects with CRp.

^c A repeat marrow should be performed to confirm relapse with 2 consecutive assessments separated by at least a month. Appearance of new dysplastic changes should be closely monitored for emerging relapse. In a subject who has been recently treated, dysplasia or a transient increase in blasts may reflect a chemotherapy effect and recovery of hematopoiesis.

CRh is defined as a CR with partial recovery of peripheral blood counts (< 5% bone marrow blasts, ANC $> 0.5 \times 10^9/L$ [500/ μL], and platelets $> 50 \times 10^9/L$ [50,000/ μL]). Because CRh is not part of modified IWG criteria, it will be derived by the Sponsor.

Table 11: Criteria for Stable Disease and Disease Progression for Acute Myeloid Leukemia

Category	Response criteria
Stable disease	Absence of CR, CRi (including CRp), PR, or MLFS and not meeting the criteria for a PD (disease progression)
Disease progression (defined only for subjects who have not previously attained CR, CRi, CRp, or MLFS)	Evidence for an increase in bone marrow blast percentage and/or increase of absolute blast counts in the blood: 
 > 50% increase in bone marrow blast count over baseline (a minimum 15% point increase is required in cases with <30% blasts at baseline); or persistent marrow blast percentage of >70% over at least 3 months; without at least a 100% improvement in ANC to an absolute level (> 500/μL, and/or platelet count to >50,000/μL non-transfused); > 50% increase in peripheral blasts (WBC \times % blasts) to >25,000/μL in the absence of treatment-related differentiation syndrome; New extramedullary disease.

Source: (Döhner et al, 2017).

Note: "Non-transfused" refers to no transfusion within 7 days of the lab assessment.

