12.5.2.2.2. DOCR, DOCRh, DOR, and DOCRI

Among subjects who achieved CR, DOCR will be calculated as the date of the first occurrence of CR to the date of first documented disease relapse, or death.

Among subjects who achieved CR or CRh, DOCRh will be calculated as the date of the first occurrence of CR or CRh to the date of first documented disease relapse or death.

Among subjects who achieved CR, CRi (including CRp), PR, and MLFS, DOR will be calculated as the date of the first response to the date of first documented disease relapse, disease progression, or death.

Among subjects who achieved CR or CRi (including CRp), DOCRI will be calculated as the date of the first occurrence of CR or CRi (including CRp) to the date of the first documented relapse or death.

Kaplan-Meier methods will be used to estimate DOCR, DOCRh, DOR, and DOCRi; subjects without relapse, disease progression, or death, as appropriate, at the time of analysis will be censored at the last response assessment date. Kaplan-Meier estimates of DOCR, DOCRh, DOR, and DOCRi will be presented by treatment arm, including estimates of the median and other quantiles, as well as individual time points (eg, 3-, 6-, and 12-month rates).

Subjects will be censored for DOCR, DOCRh, DOR, or DOCRi at the time of the start of subsequent anticancer therapy, should it occur prior to any DOCR, DOCRh, DOR, or DOCRi event, as appropriate. Detailed censoring rules will be included in the SAP. Kaplan-Meier estimates of DOCR, DOCRh, DOR, and DOCRi will be presented by treatment arm, including estimates of the median and other quantiles, as well as individual time points (eg, 3-, 6-, and 12-month rates).

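### For subjects whose only response is PR, duration of response has no loss-of-response event: a PR lost with marrow blasts back at the pretreatment level is usually stable disease, and DOR keeps running or is censored.

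*Protocol*

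**What the plan says.** - **Who is in DOR.** Protocol 6.2.2 defines "DOR, among subjects who achieved CR, CRi (including CRp), PR, and/or MLFS".
- **What ends it.** Protocol 12.5.2.2.2: "DOR will be calculated as the date of the first response to the date of first documented disease relapse, disease progression, or death". SAP 7.7.3.2 agrees, requires relapse to be confirmed, and notes under Table 8 that progression applies to subjects with a best response of PR.
- **Relapse.** Protocol Table 10: "Relapse (defined only for subjects who have previously attained CR, CRi, CRp, or MLFS".
- **PR.** Table 10 requires the blood-count criteria of CR, plus "decrease of bone marrow blast percentage to 5%-25%; and decrease of pretreatment bone marrow blast percentage by at least 50" percent.
- **Progression.** Protocol 7.1 and Table 11 give two marrow criteria. One is a ">50% increase in bone marrow blast count over baseline", with a floor of 15 percentage points when the starting value is under 30%. The other is absolute: "persistent marrow blast percentage of >70% over at least 3 months". Both are qualified by the absence of a doubling in neutrophils and/or platelets to stated levels. The other routes are a peripheral blast rise to above 25,000/µL and new extramedullary disease.
- **Stable disease.** Table 11: "Absence of CR, CRi (including CRp), PR, or MLFS and not meeting the criteria for a PD (disease progression").
- **Baseline.** SAP 6.3.4 takes the last adequate efficacy assessment on or before randomization, not the lowest value reached.
- **Censoring.** SAP Table 8 censors at the last adequate assessment showing neither relapse nor progression. This applies to subjects without an event, those starting new anticancer therapy first, and those whose event follows two or more missed assessments. SAP Table 9 labels subjects still on study with no event as ongoing.

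**The concern.** A duration-of-response endpoint should stop when the response stops. For CR, CRi, CRp and MLFS it does: relapse is reached at 5% marrow blasts. For a subject who attains PR alone, relapse is unavailable and the main marrow test for progression is anchored to the pretreatment value. Marrow blasts can therefore climb all the way back without any DOR event. A stable-disease visit after the PR is lost also counts as an assessment showing no progression, so it moves the censoring date later.

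Comparing DOR between arms is a stated objective (Protocol 6.1.2), and SAP 7.7.3.2 reports Kaplan-Meier medians and landmark rates by arm. Those summaries would include time out of response for one response category only.

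**Working it through.** The documents give no planned figure for DOR, so there is nothing to reproduce. The check applies their own criteria.

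**1. Thresholds.** Let B be baseline marrow blasts (%).
- PR ceiling = min(25, 0.5 × B), from Table 10.
- Progression by the baseline-relative criterion: above 1.5 × B; if B < 30, the rise must also be at least 15 points.

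| B | PR ceiling | Progression threshold |
|---|---|---|
| 20 | 10 | 35 (20 + 15, which exceeds 1.5 × 20 = 30) |
| 40 | 20 | 60 |
| 50 | 25 | 75 |
| 60 | 25 | 90 |
| 66.7 | 25 | 100 (cannot be exceeded) |
| 70 | 25 | 105 (cannot be exceeded) |

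A return exactly to B never exceeds 1.5 × B, so it never meets this criterion at any baseline.

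**2. Routes that remain.** A return to B can meet the absolute marrow criterion only if B is above 70%, the level persists at least 3 months, and counts have not improved as described. Peripheral blasts, extramedullary disease and death are independent of the marrow value. The count qualifier can itself block the marrow criteria: PR requires CR-level counts, so a subject who started with low counts and keeps the improvement does not meet them.

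**3. Classification.** With B = 50, PR at 20 and a later value of 50, PR is no longer met and, absent the other routes, neither is progression. Table 11 makes this stable disease, which is not an event in SAP Table 8. If new therapy then starts, the subject is censored at the last assessment without progression, which may itself fall after the PR was lost.

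**4. How many subjects.** Design rates are in Protocol 12.13.2: CR+CRh 25% vs 45% and ORR 32% vs 52% (control vs AG-120). CRh requires blasts below 5%, so PR-only subjects lie outside CR+CRh. Assuming every CRh is also counted in ORR, the residual is:
- control: 32 − 25 = 7 per 100, or 7/32 = 22% of responders;
- AG-120: 52 − 45 = 7 per 100, or 7/52 = 13% of responders.

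This is a ceiling. The residual also contains MLFS and CRi that do not meet CRh, and the documents give no separate PR rate.

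**The case against.** **Progression as the end event for PR.** It can be said that ending a PR at progression follows the response criteria that Table 11 cites, and that a study-specific loss-of-PR event is a preference. That bears on priority. It does not change the fact that time out of response is counted as response.

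**Follow-up may limit the excess.** No CR by Week 24 is treatment failure, and a response below CR after 24 weeks is a listed reason for stopping treatment (Protocol 8.5.1). EFS follow-up in 8.5.2 covers those who stop without treatment failure. Some lost PRs would therefore be censored near end of treatment. This stands in part: Protocol 10.8.1 continues assessments after discontinuation until progression or relapse, and Table 6 (footnote 14) expects subjects to remain on treatment with at least stable disease. Censoring also still leaves the loss of PR unrecorded as an event.

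**Stronger readings that the documents do not support:**
- *That relapse cannot follow a best response of PR.* Best response ranks PR above MLFS (Protocol 12.5.2.1.4, SAP 7.7.2.4). A subject with PR and then MLFS has best response PR yet has attained MLFS and can relapse. The gap concerns subjects who attain PR and none of CR, CRi, CRp or MLFS.
- *That a PR returning to baseline can never end.* The routes in step 2 can end it.
- *That control DOR is inflated more, shrinking the arm contrast.* Suppose 7 PRs per arm, a true PR median of 3 months recorded as 6 to 10, and 14.6 and 19.2 months for other responders. Exponential mixing, (1 − w) × 2^(−12/m) + w × 2^(−12/d), with w the PR share, m the other responders' median and d the PR median, moves 12-month DOR from 45.6% to 49.7–53.7% (control) and from 57.0% to 59.5–62.0% (AG-120). The difference falls from 11.4 to 8.3–9.8 points. But the PR medians and equal PR counts are assumptions. The 14.6 and 19.2 months are design medians for EFS from randomization in subjects with CR by 24 weeks, and censoring is ignored. A simple binomial 95% interval on that difference, with 32 and 52 responders, is about ±22 points.

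**Conclusion.** The gap is real and follows from the definitions alone. For PR-only subjects, a full return to pretreatment marrow blasts is usually not a DOR event, and neither document has a loss-of-PR rule.

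The impact is low. DOR is an additional secondary endpoint without alpha control (Protocol 12.5), and the SAP plans no between-arm test for it. EFS, CR rate, OS, CR+CRh rate, ORR, DOCR, DOCRh and DOCRi do not use this event. For the affected subjects recorded DOR can only be too long, but by how much, and whether the arms differ, cannot be derived. The only bound is about 7 responders per 100 in each arm, resting on the design rates and on CRh being contained in ORR.

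**What to change.** For the DOR analysis only, with all treatment rules unchanged, amend SAP 7.7.3.2/Table 8 and Protocol 12.5.2.2.2:

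1. For subjects who have attained PR and have not attained CR, CRi, CRp or MLFS, DOR ends at the earliest of: the first assessment at which the marrow part of the Table 10 PR definition is lost (blasts above 25%, or reduction from pretreatment below 50%); progression; or death.
2. Loss of PR is confirmed by the relapse rule in SAP 7.7.1.1.1: two consecutive assessments at least 4 weeks apart, or no further evaluable assessment before study discontinuation or new anticancer therapy.
3. Subjects who attain CR, CRi, CRp or MLFS at any time, including PR followed by MLFS, keep confirmed relapse (or death) as the end event. The Table 8 footnote should refer to responses attained rather than to best response.

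At minimum, prespecify this as a DOR sensitivity analysis.

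The cost is a few lines of text and one derivation from marrow data already collected. The downside is that reported DOR becomes slightly shorter and departs from a progression-only end event for PR.

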7.2. Criteria for Study Closure

This study may be prematurely closed if, in the opinion of the Sponsor, there is sufficiently reasonable cause. In the event of such action, written notification documenting the reason for study closure will be provided to each Investigator.

Circumstances that may warrant premature study closure include, but are not limited to:

- Determination of unexpected, significant, or unacceptable risk to subjects
- Failure to enroll subjects at an acceptable rate
- Insufficient adherence to protocol requirements
- Plans to modify, suspend, or discontinue the development of the study drug
- Other administrative reasons

Should the study be closed prematurely, all study materials must be destroyed or returned to the Sponsor or Sponsor's designee upon request. See Section 8.5 for specific requirements for subject termination from the study.

7.3. Temporary Modifications Allowed During Public Health Emergencies

In the event of a coronavirus disease 2019 (COVID-19) public health emergency that affects a geographic area (eg, state, province, country, region, continent) and impedes adherence to protocol-specified procedures, certain modifications (Section 7.3.1) are temporarily allowable to ensure subject safety, maintain compliance with GCP, and minimize risks to study integrity; the protocol must be followed to the fullest extent possible.

These modifications are only allowable 1) when consistent with applicable regulations and guidance and 2) for the duration of the COVID-19 public health emergency. During this period, the need for all implemented modifications will be reassessed and the Sponsor will no longer allow these modifications once the situation resolves.

Documented approval from the Sponsor is required before these modifications can be implemented.

Ivosidenib Assessment: The Sponsor has conducted a risk assessment for concomitant use of a COVID-19 vaccine with ivosidenib with specific consideration for the trial population and determined that the COVID-19 vaccine given to a trial subject is considered a simple concomitant medication with no interaction that requires advice on timing of the vaccine or other aspects that need to be mitigated.

Azacitidine Assessment: There is no known interaction (either biological or pharmacological) between investigational product and available authorized COVID-19 vaccines based on the mechanism of action and metabolism of azacitidine. There is limited data on the efficacy and safety of COVID-19 vaccines in patients with cancers, including hematologic malignancies. The efficacy and safety of vaccination in subjects who are receiving azacitidine are unknown. Currently approved or authorized COVID-19 vaccine given to a trial subject is considered as a simple concomitant medication with no anticipated interaction that requires specific advice on timing of the vaccine or other aspects during the treatment period.

7.3.1. Allowable Temporary Modifications

The following temporary modifications are allowed in the event of a COVID-19 public health emergency and must be reported as protocol deviations; refer to Schedule of Assessments (Table 6) for the timing of assessments.

- Alternative distribution of study drug
 - AG-120 may be shipped to a local healthcare provider or pharmacy or, if necessary, directly to a subject. The quantity to be shipped must be reviewed and approved in advance by the Sponsor (or designee), in agreement with the Investigator.
 - Azacitidine may **not** be shipped directly to a subject. Please refer to Section 9.7.2 (Azacitidine) for instructions on management of azacitidine.
 - Secure, trackable delivery methods (delivery service companies [eg, DHL], couriers, and hand delivery) must be used.
 - Sponsor (or designee) approval is required before each shipment. Shipment will only be permitted if, at minimum, a telemedicine visit has been conducted that incorporates appropriate safety assessments.
- Returning unused study drug, empty study drug packaging, and relevant drug diary pages
 - Return of unused study drug and empty study drug packaging may be delayed until the subject's next visit to the study site. In certain circumstances, the nature of the return process may vary (eg, personal protective equipment may be required).
 - Return of paper drug diaries may be delayed. Site, with Sponsor agreement, should provide instructions to subjects regarding timing and method for returning relevant drug diary pages.
- Telemedicine visits for assessments other than patient-reported outcomes (PROs)
 - Telemedicine visits, preferably via video conference, are permissible for all assessments that can be completed via this mode (eg, medical history, concomitant medications, review of adverse events).
- Use of laboratories and healthcare providers not specified in the clinical trial documentation
 - For assessments that cannot be completed via telemedicine, the use of healthcare providers and laboratories that are not specified in the clinical trial documentation (eg, an imaging facility, clinic, or local practice that is more readily accessible by the subject) is permissible for all assessments that can be completed via this mode (eg, blood collection for laboratory assessments, ECG, physical examinations, imaging).

- Use of a laboratory or healthcare provider not specified in the clinical trial documentation requires coordination between the subject, the investigator, and the subject's local healthcare provider.
- The investigator must document their review of the results provided by laboratories and healthcare providers not specified in the clinical trial documentation.
- Home health study support
 - For assessments that cannot be completed via telemedicine, home healthcare provider visits are permissible for all assessments that can be completed via this mode (eg, physical examination, collection of clinical laboratory samples).
 - The Sponsor may facilitate and coordinate these visits with the study site.
 - The Investigator must document their review of the results of home healthcare provider visits.
- Virtual informed consent in lieu of in-person informed consent
 - Reconsent (ie, consenting to an amended version of the protocol) may be completed virtually and documented in the relevant subject medical records. In these instances, reconsent may be completed virtually where allowed by the applicable regulations, and documented in the relevant subject medical records.

